
 • To evaluate the efficacy of RPT193 administered orally QD for 16 weeks to subjects with moderate-to-severe AD on subject reported symptoms associated with AD. 	
 • Change from baseline to Week 16 in: 
 ○ Sleep quality (visual analog scale [VAS] from SCORAD) ○ Patient-oriented eczema measure (POEM) ○ Dermatology Quality of Life Index (DLQI) ○ Skin pain NRS ○ Patient global assessment (PtGA). ○ Atopic dermatitis sleep scale (ADSS) ○ 

Objectives	Endpoints
	
 ○ Asthma Control Questionnaire (ACQ-5) (in subjects with a history of asthma) ● % of subjects achieving a PtGA score of 0 or 1 and a ≥ 2 point reduction from baseline at Week 2, 4, 8, 12, and 16.

 ● To evaluate the efficacy of RPT193 administered orally QD for 16 weeks to subjects with moderate-to-severe AD in subject subpopulations. 	
 ● % change in EASI in the following subgroups: 
 ○ Prior treatment with dupilumab or tralokinumab (Yes or No) ○ Baseline EASI score of < 21 or ≥ 21 ○ Baseline %BSA of AD affected skin $< 50\%$ or $\geq 50\%$ ○ Baseline vIGA score (3 or 4) ○ Age group ○ Race ○ Ethnicity ○ Pretreatment CCL17 levels ○ Pretreatment CCL22 levels.

 ● Explore durability of treatment effect in those who have demonstrated an objective response at Week 16. 	
 ● Proportion of subjects maintaining EASI-50 at Weeks 18, 20, 24 among those achieving an EASI-50 at Week 16 and not receiving rescue therapy from Week 8 to Week 16. ● Proportion of subjects maintaining EASI-75 at Weeks 18, 20, 24 among those achieving an EASI-75 at Week 16 and not receiving rescue therapy from Week 8 to Week 16. ● Proportion of subjects maintaining EASI-90 at Weeks 18, 20, 24 among those achieving an EASI-90 at Week 16 and not receiving rescue therapy from Week 8 to Week 16. ● Proportion of subjects maintaining a vIGA score of 0 or 1 at Weeks 18, 20, 24 among those achieving a vIGA score 0 or 1 at Week 16 and not receiving rescue therapy from Week 8 to Week 16.

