5.1 Inclusion Criteria

Subjects are eligible to be included in the study only if all of the following criteria apply:

1. Male or female subject aged 18 to 75 years, inclusive, at the time of consent.
2. Subject has clinically confirmed diagnosis of active AD, according to the revised Hanifin and Rajka criteria. [Eichenfield 2014]
3. Subject has at least a 12-month history of AD and had no significant flares in AD for at least 4 weeks before Screening, as determined by the Investigator through subject interview at the Screening visit or information obtained from medical chart or subject's physician.
4. Subject has a documented history of inadequate response to a ≥ 1 month treatment with topical medications, such as class I-V topical corticosteroids, topical PDE4 inhibitor (e.g., crisaborole), and/or calcineurin inhibitors in the 6 months prior to the Screening visit or subjects for whom topical treatments are otherwise medically inadvisable.
5. Subject has AD covering $\geq 10\%$ of the BSA.
6. Subject has an EASI score ≥ 16 at Screening and at Baseline.
 - Subjects may be screened with an EASI score ≥ 12 if the subject is administering class I-V topical corticosteroids, topical PDE4 inhibitor (e.g., crisaborole), and/or topical calcineurin inhibitors or is using systemic immunosuppressants (e.g., methotrexate, cyclosporine A, mycophenolic acid, azathioprine, and/or systemic corticosteroids); eligibility for the study requires follow-up EASI score ≥ 16 at Baseline (after the relevant washout period for the index medication has been satisfied).
7. Subject has a Validated Investigator Global Assessment (vIGA) score ≥ 3 .
8. Subject has been using one or more emollient(s) (except urea-containing emollients or medicated emollients that are regulated as a medical device) at least twice daily for 1 week prior to Baseline (except on visit day before the visit) and agrees to continue using the same emollient(s) daily at the same frequency (at least twice daily) throughout the study.

Notes: On the day of scheduled visit, subjects cannot apply emollient before their scheduled visit, and every effort should be made to use the same emollient throughout the study for the same body region. However, the chosen emollient may differ depending on the body region (e.g., body vs face emollient may be different).
9. Female subject of childbearing potential has had a negative serum pregnancy test at Screening and negative urine pregnancy test at Baseline.

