### C. Changes to Planned Analyses from Protocol

The following changes or additions to the planned analyses described in the protocol are noted:

- In Protocol Amendment v2.0, the randomization list is stratified based on region (North America vs. rest of world), baseline vIGA scores (vIGA of 3 vs. 4), and prior dupilumab or tralokinumab use (yes or no). It was later determined that no subjects will be recruited from rest of the world, and therefore stratifying by region in randomization will no longer be required. The existing randomization master list including region as a stratification factor will not be modified or replaced. Any strata related to rest of world region will be disregarded by the IWRS in assigning randomized treatment. All statistical analyses will be adjusted to align with this change by removing region as a stratification factor as applicable.
- Subgroup analysis by pretreatment CCL17/22 levels as required by the protocol is

[REDACTED] ( [REDACTED] ) not included in this SAP. This analysis will be covered by a separate analysis plan for PD data.

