### A. Estimand

The main estimands associated with the primary and key secondary endpoints to support regulatory decisions are described in the following table:

Attribute	Description
Treatment	RPT 193-02 (50mg, 200mg, 400mg) and Placebo
Population	Adult subjects with moderate-to-severe AD as defined by the inclusion/exclusion criteria
Endpoint	
Primary Endpoint
 
 
% change in Eczema Area Severity Index (EASI) from baseline at Week 16
 
 
Key Secondary Endpoints
 
 
% of subjects achieving a Validated Investigator Global Assessment (vIGA) score of 0 or 1 at Week 16
 
% of subjects achieving EASI-75, defined as a 75% reduction in EASI from baseline to Week 16
 
% change from baseline in PP-NRS from an itch daily e-Diary at Week 16.
 

Intercurrent Events	
 
Early termination of study treatment: Subjects who discontinue from the study treatment prior to Week 16 will be analyzed by the treatment policy strategy, i.e., all data collected after termination of study treatment but prior to rescue medication will be included in the analysis. Missing post discontinuation values will be imputed according to details provided below.
 
Use of rescue medications: Subjects who use rescue medication during the 16-week treatment period will be analyzed by the hypothetical strategy. All EASI/vIGA/PP-NRS scores collected after the start of rescue medication will be set to missing. The missing data after the use of rescue medication will be imputed to follow a similar profile as the placebo group.
 

Population-level Summary	
Primary Endpoint
 
 
Difference in mean percent change from baseline in EASI score between each RPT193 dose and placebo at Week 16.
 
 
Key Secondary Endpoints
 
 
Difference in percentage of subject achieving vIGA of 0 or 1 between each RPT193 dose and placebo at Week 16.
 
Difference in percentage of subject achieving EASI-75 between each RPT193 dose and placebo at Week 16.
 
Difference in mean percent change from baseline in PP-NRS
 

	between each RPT193 dose and placebo at Week 16.
--	--

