## E. Exploratory Efficacy Analysis

All exploratory efficacy analysis will be based on the FAS. Descriptive summary statistics will be provided by treatment and visit for exploratory endpoints listed below. No imputation will be utilized for missing data.

- Percent change in SCORAD from baseline at Week 2, 4, 8, 12, and 16
- Percent change in BSA from baseline at Week 2, 4, 8, 12, and 16
- Change from baseline to Week 16 in sleep loss from the SCORAD VAS
- Change from baseline to Week 16 in POEM
- Change from baseline to Week 16 in DLQI
- Change from baseline to Week 16 in Skin pain NRS
- Change from baseline to Week 16 in PtGA  
A shift table from baseline will be provided.
- Change from baseline to Week 16 in ADSS  
For item 1 and 3 a shift table will be provided to display the change from baseline. The change from baseline for item 2 will be presented descriptively.

- Change from baseline to Week 16 in ACQ-5  
A shift table from baseline will be provided for each question
- Percent of subjects achieving a PtGA score of 0 or 1 and a  $\geq 2$  point reduction from baseline at Week 2, 4, 8, 12, and 16. The assessment at each specific timepoint will be independently considered.
- Subgroup analysis of the primary efficacy endpoint as outlined in section IV.I
- Proportion of subjects maintaining responder status at Weeks 18, 20, 24 among those achieving the corresponding responder status at Week 16 and not receiving rescue therapy from Week 8 to Week of interest. The endpoint at Week 20 will not consider Week 18 status and will include subjects that do not use rescue from Week 8 to Week 20. Similarly, Week 24 will not consider responder status at Week 18 and Week 20 and will only include subjects that did not use rescue from Week 8 to Week 24. An additional analysis will be conducted without consideration of the use of rescue medication after Week 16. The following responder status will be analyzed separately.
  - EASI-50
  - EASI-70
  - EASI-90
  - vIGA score of 0 or 1
- Percent change in EASI at Weeks 18, 20, and 24 compared to Week 16 among those not receiving rescue therapy from Week 8 to Week of interest. In other words, the analysis at Week 20 will only include subjects who do not use rescue from Week 8 to Week 20.
- Percent change in SCORAD at Weeks 18, 20, and 24 compared to Week 16 among those not receiving rescue therapy from Week 8 to week of interest.

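### SAP Section VI.E lists maintenance of EASI-70, an undefined response level, where the protocol and the SAP's own endpoint table specify EASI-75

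*Protocol*

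**What the plan says.** The protocol synopsis and Protocol Table 1 set four maintenance endpoints for the period after treatment stops: EASI-50, EASI-75, EASI-90 and vIGA 0/1, each assessed at Weeks 18, 20 and 24 among Week 16 responders. The EASI-75 item reads "Proportion of subjects maintaining EASI-75 at Weeks 18, 20, 24 among those achieving an EASI-75 at Week 16", with a further condition on rescue use. SAP Section II carries over the same four.

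SAP Section VI.E turns these into an analysis. It opens with "Descriptive summary statistics will be provided by treatment and visit for exploratory endpoints listed below". Under the maintenance item it says "The following responder status will be analyzed separately" and then names EASI-50, EASI-70, EASI-90 and vIGA 0/1. EASI-75 is missing from that list.

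Elsewhere the SAP uses EASI-75 consistently. The estimand table in SAP II.A gives the key secondary endpoint as the percentage "of subjects achieving EASI-75, defined as a 75% reduction in EASI from baseline to Week 16".

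**The concern.** EASI-70 occurs only in SAP VI.E and has no definition in either document. If the tables follow that list, the protocol's EASI-75 maintenance endpoint is replaced by one at a different cut.

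EASI-75 at Week 16 is a key secondary endpoint, and both documents give sustained response after the end of dosing as a reason for the 8-week follow-up. Maintenance of EASI-75 is the result that connects the two. An EASI-70 maintenance rate starts from a different group of responders and applies a different threshold. It therefore cannot be read beside the Week 16 EASI-75 rate or reported as the protocol endpoint.

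**Working it through.** **1. The lists side by side**

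| Place | Response levels for maintenance |
|---|---|
| Protocol 1.1 Synopsis | EASI-50, EASI-75, EASI-90, vIGA 0/1 |
| Protocol 3.0, Table 1 | EASI-50, EASI-75, EASI-90, vIGA 0/1 |
| SAP II endpoint table | EASI-50, EASI-75, EASI-90, vIGA 0/1 |
| SAP VI.E analysis list | EASI-50, **EASI-70**, EASI-90, vIGA 0/1 |

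**2. Is the change declared?** SAP I.C begins "The following changes or additions to the planned analyses described in the protocol are noted". It lists two items: region is dropped as a stratification factor, and the CCL17/CCL22 subgroups move to another plan. Neither concerns the response level.

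**3. Is EASI-75 maintenance analysed elsewhere in the SAP?** The EASI-75 analyses in SAP VI.B and VI.D cover Week 16 (key secondary), Weeks 2 to 16 (other secondary) and time to first response. None covers maintenance of a Week 16 response at Weeks 18, 20 and 24.

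**4. What the different cut does to one subject.** Reading EASI-70 as a reduction of at least 70% is an assumption, since it is undefined. The ceilings for response are then:

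- EASI-75: score ≤ (1 − 0.75) × baseline = 0.25 × baseline
- EASI-70: score ≤ (1 − 0.70) × baseline = 0.30 × baseline
- Ratio: 0.30 / 0.25 = 1.2, so the EASI-70 ceiling is 20% higher at every baseline.

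The lowest eligible baseline comes from Protocol 5.1: "Subject has an EASI score ≥ 16 at Screening and at Baseline". At baseline 16 the ceilings are 4.0 and 4.8; at baseline 30 they are 7.5 and 9.0. A subject with baseline 16 and a later score of 4.5 has improved by (16 − 4.5)/16 = 71.9%. That subject is a responder at EASI-70 and not at EASI-75.

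**5. What it does to the Week 16 denominator.** The sample-size inputs are redacted, so the distribution has to be assumed: percent change normal with mean −40 to −60 and SD 30 to 40. The share of EASI-70 responders who are not EASI-75 responders is 1 − Φ((−75 − mean)/SD) / Φ((−70 − mean)/SD).

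- Mean −50, SD 35: Φ(−0.714) = 0.238 and Φ(−0.571) = 0.284. The share is 1 − 0.238/0.284 = 16%. With 67 per arm that is 15.9 against 19.0 responders.
- Smallest share on the grid (mean −60, SD 40): 1 − 0.354/0.401 = 12%.
- Largest share on the grid (mean −40, SD 30): 1 − 0.122/0.159 = 23%.

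These figures describe the denominator only. They take no account of the exclusion of rescued subjects, and they do not estimate the maintenance proportion itself.

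**The case against.** The best counter-argument is that this is one mistyped digit. SAP II still carries EASI-75, the VI.E list otherwise matches it item for item, and the SAP has other slips of the same sort, such as an EASI area band printed as 30-29%. A programmer who met an undefined level would be expected to query it, and the table shells, which are not available here, may already be right. That explanation is probably correct, and it means that non-production of the endpoint can be asserted only for VI.E as written. It does not remove the need for a correction, because VI.E is the analysis instruction and it contradicts SAP II.

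The stakes are also limited. The endpoint is exploratory, descriptive, not imputed and outside the multiplicity procedure. The Week 16 EASI-75 analysis is untouched. Durability is still described by EASI-50, EASI-90 and vIGA 0/1 maintenance and by percent change in EASI and SCORAD from Week 16. Composite EASI scores are listed by subject, so the EASI-75 result could be derived later. All of this stands.

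The direction of bias in the maintenance rate is not fixed. A subject going from 76% to 71% improvement is kept under EASI-70 and lost under EASI-75. A subject going from 72% to 68% is lost under EASI-70 and never enters the EASI-75 denominator. This also stands: the two rates differ, but not predictably in one direction.

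The normal model is crude, since percent change cannot fall below −100 and at mean −50, SD 35 about 7.7% of the curve does. Placing that mass at −100 leaves the share at 16%. Discarding it gives (0.284 − 0.238)/(0.284 − 0.077) = 22%. In this example the crude model does not overstate the share.

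Finally, the protocol already fixes 75, so a late correction would leave little freedom of choice. SAP IV.F restricts the Week 16 results to a small unblinded group without subject-level data, and SAP I.B requires later deviations to be documented. The concern about choosing the cut with results known is therefore minor.

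**Conclusion.** The concern holds. The response level in SAP VI.E contradicts the protocol synopsis, Protocol Table 1 and SAP II; it is undefined and undeclared. Followed literally, the SAP gives no EASI-75 maintenance analysis and applies a 70% cut to both the denominator and the maintenance criterion.

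The 20% difference in the score ceiling follows directly once EASI-70 is read as a 70% reduction. The 12% to 23% shift in the denominator also rests on the assumed normal distribution and is an illustration only. Because the endpoint is exploratory and the likely cause is a typing error, this is a correction that should be made; it does not threaten the trial's main inference.

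**What to change.** In the maintenance list of SAP VI.E, replace EASI-70 with EASI-75, stated as a reduction from baseline of at least 75% both at Week 16 and at the follow-up visit of interest. Check that the table shells and programming specifications use the same cut.

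If an EASI-70 analysis is intended, keep it in addition to EASI-75, define it, and record it in SAP I.C.

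The cost is one line of SAP text and one programming parameter. It should be done before treatment unblinding, and preferably before the Week 16 results are released to the unblinded group.

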33. Subject is not willing to minimize natural and artificial sunlight exposure during the study. Use of sunscreen products and protective apparel are recommended when sun exposure cannot be avoided.
34. Subject is not willing to maintain their baseline skin care regimen (e.g., bathing) or use of herbals and/or supplements through the duration of the study.
35. Subject who is still participating in a clinical trial or who has participated in a clinical trial within 1 month prior to the Screening visit.

Note: Please also refer to Exclusion Criteria 15 and 16 regarding those who participated in an investigational clinical trial.

Statistical methods:

Continuous endpoints will be summarized using descriptive statistics (number of subjects [n], mean, standard deviation [SD], median, minimum, and maximum). Categorical endpoints will be summarized using frequency counts and percentages. All individual subject data will be present in listings.

Analysis sets will include a Full Analysis Set, a Per-Protocol Analysis Set, and a Safety Analysis Set.

The primary efficacy endpoint is the percent change from baseline in EASI score at Week 16. The primary analysis will be performed in FAS. The primary efficacy endpoint will be analyzed with analysis of covariance (ANCOVA) model. The model will include treatment group (each RPT193 dose vs. placebo), baseline vIGA scores, randomization stratification factors and study sites as factor, and baseline EASI score as a covariate. The least square (LS) mean and LS mean difference along with the 95% confidence interval (CI) and p-value will be reported.

For continuous secondary endpoints, the same model as discussed for the primary analyses will be followed. For binary secondary endpoints, a logistic regression model with treatment group, baseline vIGA scores, randomization stratification factors, study sites as factors and baseline score as a covariate will be used.

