9.4.2 Primary Efficacy Analysis

The primary efficacy endpoint is the percent change from baseline in EASI score at Week 16.

The primary estimand is defined as

- Population of interest: adult subjects with moderate-to-severe AD as defined by the inclusion/exclusion criteria
- Variable/endpoint of interest: percent change from baseline in EASI score at Week 16.
- Intercurrent event handling strategy:
 - Early termination of study treatment: subjects who discontinue from the study treatment prior to Week 16 will be analyzed by the treatment policy strategy, i.e., all data collected will be included in analysis.
 - Use of rescue medications: subjects who use rescue medication during the 16-week treatment period will be analyzed by the hypothetical strategy. All EASI scores collected after the start of rescue medication will be set to missing and imputed.
- Population-level summary measure: difference in mean percent change from baseline in EASI score between RPT193 and placebo.

The primary analysis will be performed in FAS. The primary efficacy endpoint will be analyzed with ANCOVA model. The model will include treatment group (each RPT193 dose vs. placebo), baseline vIGA scores, randomization stratification factors and study sites as factor, and baseline EASI score as a covariate. The least square (LS) mean and LS mean difference along with the 95% confidence interval (CI) and p-value will be reported.

The following sensitivity analysis will be planned for the primary estimand:

- In FAS, including only the observed data regardless of rescue medication uses and without missing data imputation.
- In PP analysis set, following the same model as described for the primary estimand.

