The missing EASI, and PP-NRS values will be imputed 100 times to generate 100 complete data sets by using the Markov Chain Monte Carlo (MCMC) method implemented with the SAS PROC MI procedure. The example code can be found in Appendix II.

100 imputed datasets will be generated following the 2 steps below:

1. The monotone missing pattern is induced by Markov Chain Monte Carlo (MCMC) method in MI procedure. The monotone missing pattern means that if a subject has missing value for a variable at a visit, then the values at all subsequent visits for the same variable are all missing for the subject.
2. The missing data at subsequent visits will be imputed using the regression method for the monotone pattern with adjustment for covariates including treatment groups, the randomization stratification factors of baseline vIGA score (3,4), and prior dupilumab or tralokinumab use (yes or no), and relevant baseline value.

These completed datasets are then analyzed using standard analysis methods and results combined (averaged) to present one MI result.

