### C. Primary Efficacy Analysis

The primary endpoint is the percent change in EASI from baseline to Week 16. The primary analysis will be based on the FAS and will use control-based PMM-MI to handle missing data.

The primary efficacy endpoint will be analyzed with an ANCOVA model. The model will include treatment group (each RPT193 dose vs. placebo), the randomization stratification factors of baseline vIGA score (3,4), and prior dupilumab or tralokinumab use (yes or no), and baseline EASI score as a covariate.

For each imputed dataset the least square (LS) mean, and LS mean difference in the percent change from baseline between each RPT193 dose level and placebo along with the corresponding estimated standard error will be reported. These results will be combined in PROC MIANALYZE using Rubin's formula and the resulting p-value will be used for inference at the 0.05 level of significance. The LS mean and LS mean difference along with the 95% confidence interval (CI) and p-value will be reported.

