### Continuous endpoint

The continuous endpoint will be analyzed in a similar manner as the primary efficacy endpoint.

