### Sensitivity Analyses

Similar to primary efficacy endpoint, missing PP-NRS will be imputed using the multiple imputation (MI) with analysis of covariance (ANCOVA) model. MI will be performed under missing at random (MAR) assumption.

The Week 16 data of each of the 100 complete imputed datasets will be analyzed using an ANCOVA model with treatment, randomization strata, and baseline PP-NRS value included in the model, and the SAS MIANALYZE procedure will be used to generate valid statistical inferences by combining results from the 100 analyses using Rubin's formula.

The percent change from baseline in PP-NRS will also be analyzed using MMRM without imputation. The model will include factors (fixed effects) for treatment, randomization strata, visit, treatment-by-visit interaction, and baseline PP-NRS score. An unstructured covariance matrix will be used to model the within-patient errors. Denominator degrees of freedom will be estimated using approximation of SATTERTH. The efficacy data will be set to missing after rescue medication or procedure is used or after study withdrawal. Afterwards no imputation will be made.

The MMRM model will provide baseline adjusted least-squares (LS) means at Week 16 and at other time points for each treatment group with the corresponding standard error and the confidence interval, as well as the p values for treatment comparisons. The graph of LS-mean +/- SE by visit will be provided.

Other following sensitivity analyses will be planned for the key secondary using the ANCOVA or logistic model mentioned above, as applicable:

- In FAS, using PMM-MI and including site as a factor in the ANCOVA model.
- PP analysis set, using MI for handling missing data for all key secondary endpoints.
- In FAS, the LOCF and WOCF methods for handling missing data for continuous endpoints.

- In FAS, the TF method for handling missing data for binary endpoints.
- In FAS, the Observed-Cases (OC) approach for all endpoints. No imputation for missing data at any time point.

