### SAS example code for PMM-MI (NMAR):

#### EASI\_PP-NRS

```
proc mi data =data_in out =data_out seed=1277282 nimpute = 1 min=0 by _imputation_;  
  class trt01p base_VIGA prioruse;  
  var base_EASI week2-16;  
  monotone reg(week16 = base_EASI week2-12 trt01p base_VIGA prioruse);  
  mnar model(week16/ modelobs=(trt01p='placebo'));  
run;
```

VIGA

```
proc mi data =data_in out =data_out seed=1277282 nimpute = 1 min=0 max=4
  by _imputation_;
  class trt01p base_VIGA prioruse;
  var base_VIGA week2-16;
  monotone_logistic(week16 = week2-12 trt01p base_VIGA prioruse);
  mnar model(week16/ modelobs=(trt01p='placebo'));
run;
```

SAS example code for imputed results combinations:

```
proc glm data = data_mi;
  model week16 = base_EASI week2-12 trt01p base_VIGA prioruse;
  by _imputation_;
  ods output ParameterEstimates=mxparms;
run;

proc mi analyze parms=mxparms;
  class trt01p;
  modeleffects Intercept base_EASI week2-12 trt01p base_VIGA prioruse;
run;
```

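### The SAP does not name the baseline covariate for the main analysis of percent change in PP-NRS; taken literally, the protocol wording and the example imputation code use baseline EASI, not baseline itch.

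*Protocol*

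**What the plan says.** **Protocol.** The synopsis and section 9.4.2.1 both state: "For continuous secondary endpoints, the same model as discussed for the primary analyses will be followed". Section 9.4.2 gives that model's terms as treatment, baseline vIGA, "randomization stratification factors and study sites as factor, and baseline EASI score as a covariate".

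**SAP, main analysis.** Section VI.C repeats the primary ANCOVA without study site, "and baseline EASI score as a covariate". For percent change in PP-NRS, section VI.D.1 (Continuous endpoint) says in full: "The continuous endpoint will be analyzed in a similar manner as the primary efficacy endpoint". No covariate is named. Sections VI.B and VI.D.1 make control-based PMM-MI the main missing-data method for this endpoint. The one Appendix II block for that method headed for EASI and PP-NRS together has the regression "monotone reg(week16 = base_EASI week2-12 trt01p base_VIGA prioruse". Its VAR list holds `base_EASI` and the post-baseline weeks, with no baseline PP-NRS. The code for combining imputed results also uses `base_EASI`.

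**SAP, sensitivity analyses.** Section VI.D.1 specifies for PP-NRS an "ANCOVA model with treatment, randomization strata, and baseline PP-NRS value included in the model", and an MMRM with "treatment-by-visit interaction, and baseline PP-NRS score". In section IV.D.2 the imputation under MAR, which covers EASI and PP-NRS, adjusts for treatment, the stratification factors "and relevant baseline value".

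**The concern.** The endpoint divides by baseline PP-NRS. Under SAP IV.C that baseline is the Day 1 assessment, whereas Week 16 is the mean of at least three daily entries over Days 107 to 113. A single noisy denominator tends to correlate with the percent change: a high Day 1 entry yields a larger apparent fall. The inclusion criteria set no minimum PP-NRS, so low baselines are possible. Baseline itch is therefore a natural covariate, and it is already collected.

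If a programmer follows the explicit instructions that reach the main analysis, three things follow:

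- The model adjusts for another instrument's baseline and forgoes whatever precision baseline itch would bring.
- Main and sensitivity results differ in covariate as well as in the handling of missing data, so a difference between them cannot be attributed to the missing-data assumption alone.
- A subject with little post-baseline diary data has Week 16 itch imputed without reference to baseline itch, and the result is then divided by that baseline.

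The wording also lets two programmers fit different models to a key secondary endpoint and both claim to follow the plan.

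**Working it through.** **The plan's own figure.** The sample size rests on 60 evaluable per group and 10% dropout: 60 / 0.9 = 66.7, so 67 per group, and 4 × 67 = 268, as in the SAP (the protocol says approximately 265). It is sized on EASI; the effect size, SD and power are redacted. Neither document gives a precision or power figure for PP-NRS, so there is none to reproduce.

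**Cost of the wrong baseline in the ANCOVA.** Let r be the within-arm correlation of baseline PP-NRS with percent change in PP-NRS, and q the correlation of baseline EASI with baseline PP-NRS. The documents give neither, so both are assumed. If baseline EASI relates to the outcome only through baseline itch, then

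SE with baseline PP-NRS / SE with baseline EASI = √[(1 − r²) / (1 − (rq)²)].

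With q = 0 the variance falls by r², and the effective n per arm is 60 / (1 − r²). The power column assumes 80% power without the itch covariate, that is, a standardised effect of (1.960 + 0.842) × √(2/60) = 0.5115.

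| r | SE ratio, q = 0 | Variance saved, q = 0 | Effective n | Power | SE ratio, q = 0.3 |
|---|---|---|---|---|---|
| 0.1 | 0.995 | 1% | 60.6 | 80.4% | 0.995 |
| 0.2 | 0.980 | 4% | 62.5 | 81.6% | 0.982 |
| 0.3 | 0.954 | 9% | 65.9 | 83.6% | 0.958 |
| 0.4 | 0.917 | 16% | 71.4 | 86.4% | 0.923 |
| 0.5 | 0.866 | 25% | 80.0 | 89.9% | 0.876 |

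Example for q = 0.3, r = 0.5: √[0.75 / (1 − 0.0225)] = √(0.75 / 0.9775) = 0.876.

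**Check by simulation.** With 60 per arm and 1,500 trials per setting, the simulated SE ratios at q = 0 were 0.993, 0.949 and 0.869 for r = 0.1, 0.3 and 0.5; at q = 0.3 they were 1.003, 0.973 and 0.880. With no true effect, the mean estimated difference lay within 0.008 of zero under either covariate, against an SD of about 0.16 to 0.19. The choice affects precision, and no bias appears.

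**Simulation on the itch scale.** This assumed 67 per arm, true itch mean 7 with SD 1.3 to 1.8, Day 1 noise SD 0.5 to 1.5, an EASI–itch correlation of 0.25 and an 18-point effect, with 3,000 trials per setting. The variance ratio ran from 0.991 to 0.845, a saving of about 1% to 15%. Power rose by about 0 to 7 points (for example 69.5% to 72.6% at noise SD 1.25 and itch SD 1.8).

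**Imputation.** The quoted regression includes the subject's own scores at weeks 2 to 12, which carry much of the baseline information. The gap therefore concerns mainly subjects with few or no usable diary weeks, for whom `base_EASI` is the only continuous baseline score. In the extreme case, suppose a Week 16 score of 5.5 (assumed) is drawn regardless of own baseline. Percent change is then (5.5 − 4) / 4 = +38% for a baseline of 4, and (5.5 − 10) / 10 = −45% for a baseline of 10.

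**The case against.** A reader might infer that the plan definitely leaves baseline itch out and specifies the wrong covariate. The documents do not support that:

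- SAP VI.D.1 asks for similarity to the primary analysis, not identity. The only ANCOVA it spells out for PP-NRS contains baseline PP-NRS, in wording parallel to the EASI version in VI.C.
- SAP IV.D.2 calls for the baseline relevant to the endpoint under MAR and introduces the control-based procedure as similar to the MAR one. The binary endpoints likewise take their own baseline score.
- Appendix II is labelled example code and is generic. Its ANCOVA names a vehicle reference group in a placebo-tablet trial. Its MMRM shows only `base_EASI`, although VI.D.1 plainly requires baseline PP-NRS in the PP-NRS MMRM. The joint imputation block must be adapted in any case, because IV.D.2 imputes every weekly PP-NRS visit.
- The protocol sentence is a summary. Protocol 9.1 leaves detail to the SAP, which by its section I.B governs the analysis and already departs from the protocol model by dropping site and region.

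All of this stands, and it makes endpoint-specific baselines the likely intent. It does not close the gap, because no sentence names the covariate for the main PP-NRS analysis and the only code for its main imputation method points to EASI. Intent that must be inferred is not prespecification.

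A reader might also infer a biased result or a known loss of power. Neither is shown. The size depends on correlations that the documents do not give, and that baseline EASI says little about itch is itself an assumption.

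**Conclusion.** The point holds as an ambiguity and a mismatch between text and example code in a key secondary analysis. Followed literally, the main PP-NRS analysis would forgo about 1% to 15% of variance in the itch-scale simulation, or 1% to 25% over r = 0.1 to 0.5 with q = 0. If percent change is nearly unrelated to baseline itch, the loss is negligible. The lack of comparability with the sensitivity analyses follows from the literal reading whatever the correlation. The imputation weakness is confined mainly to subjects with little or no post-baseline diary data.

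The complete-data ANCOVA shows no bias, the primary EASI analysis is unaffected, and SAP IV.G places PP-NRS outside the error-controlled sequence. Severity is low to moderate.

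**What to change.** Change the SAP only:

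- In VI.D.1 (Continuous endpoint), state that the model is the primary ANCOVA with baseline PP-NRS in place of baseline EASI.
- In Appendix II, give PP-NRS its own imputation and analysis block, with baseline PP-NRS in the VAR list, as a predictor in the imputation regression, and as the ANCOVA covariate.

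The cost is one sentence and one code block; the Day 1 score is already collected. SAP I.B allows changes until unblinding. Under IV.F the key secondary results go to a limited unblinded sponsor group after the last subject completes Week 16, so the change should be made before then. Because the SAP governs, no protocol amendment is needed for this alone. The protocol sentence can be aligned if it is amended for other reasons.
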